#### **8.1.6. Pregnancy Testing**

Subjects who are WOCBP should have a UPT performed early in the screening procedures (following informed consent) which shows negative results in order to avoid the continuation of what would then be unnecessary screening testing. Subjects who are WOCBP must also have a negative serum pregnancy test result from Screening (Visit 1) to continue in the study, and a negative UPT at Baseline (Visit 2) prior to randomization. In addition, the investigator or designee will perform a urine pregnancy test for subjects who are WOCBP at the visits detailed in Schedule of Assessments ([Table 3](#)). The UPT kits provided by the Central lab have a minimum sensitivity of 25-mIU  $\beta$ -HCG/milliliter (mL) of urine. If the result of any post-

treatment urine pregnancy test is positive, the subject will be withdrawn from the study and the subject's pregnancy documented and followed.

### **8.1.7. Pharmacokinetic Assessments**

At selected sites, a qualified staff member will collect a 4.5 mL sodium citrate vacutainer for analysis of ATI-502 predose at Visit 2 and at Visits 4, 6, and 9, 12 hours ( $\pm$  30 minutes) after the prior evening dose. Samples will be sent to a bioanalytical laboratory for analysis. Refer to the pharmacokinetic laboratory manual for handling and shipping instructions.

## **8.2. Adverse and Serious Adverse Events**

Adverse events will be monitored throughout the study and reported on the appropriate Aclaris Therapeutics, Inc. AE eCRF.

### **8.2.1. Definition of Adverse Events**

#### **8.2.1.1. Adverse Event (AE)**

An AE is the development of an undesirable medical condition or the deterioration of a pre-existing medical condition following or during exposure to a pharmaceutical product, whether or not considered casually related to the product.

The investigator should, when certain, report a diagnosis rather than the signs, symptoms or clinically significant abnormal laboratory values associated with the AE. Otherwise, signs, symptoms or abnormal laboratory values may be used to describe the AE.

Every new episode or clinically significant worsening of a chronic condition (e.g., headaches, seasonal allergies, depression, or hypertension) should be reported as a separate AE, even if the condition is reported in the subject's medical history. Hair growth in unexpected areas, such as facial hair in women, should be reported as an adverse event.

Any CS abnormality discovered prior to the first study medication treatment should be reported as medical history, not as an AE.

All AEs that occur after any subject has been enrolled, before treatment, during treatment, or within 30 days following the cessation of treatment, whether or not they are related to the study, must be recorded in the subject's source documents and in the Aclaris' electronic case report form (eCRF). Changes to a subject's medical condition that occur between signing an ICF and beginning treatment should be captured in the medical history.

#### **8.2.1.2. Serious Adverse Event (SAE)**

A serious adverse event is an AE occurring during any study phase (i.e., Baseline, Treatment, Washout, or Follow-up), and at any dose of the investigational product, comparator or placebo, that fulfills one or more of the following:

- Results in death
- It is immediately life-threatening
- It requires in-patient hospitalization or prolongation of existing hospitalization

- It results in persistent or significant disability or incapacity
- Results in a congenital abnormality or birth defect
- It is an important medical event that may jeopardize the patient or may require medical intervention to prevent one of the outcomes listed above.

The term “life threatening” refers to an event in which the subject was at risk of death at the time of event; it does not refer to an event that hypothetically might have caused death if it were more severe.

Important medical events are those that may not be immediately life threatening, result in death or hospitalization, but are clearly of major clinical significance and may jeopardize the subject or require intervention to prevent one of the outcomes listed in the SAE definition above. These should also usually be considered serious.

All SAEs that occur from the time of informed consent until 30 days following the cessation of study medication dosing, whether or not they are related to the study, must be recorded on the SAE forms provided by Aclaris Therapeutics, Inc.

#### **8.2.1.3. Unexpected adverse event**

An AE is considered unexpected if it is not listed in the Investigator’s Brochure or is not listed at the specificity or severity that has been observed.

### **8.3. Reporting Adverse Events**

#### **8.3.1. Adverse event reporting period**

The investigator must start reporting non-serious AEs from the time of the subject’s first dose of study medication until 30 days after the last dose of study medication. Reporting for SAEs must start when the subject signs the ICF and continue until 30 days past the subject’s last dose of study medication, whether or not they are related to the study.

#### **8.3.2. Severity**

The investigator is to define the severity of each AE using the following definitions as a guideline. The investigator will consider the range of the possible severity of the event and identify the severity that is the most appropriate according to her/his medical judgment.

**Mild** – Awareness of signs or symptom, but easily tolerated

**Moderate** – Discomfort, enough to cause interference with usual activity

**Severe** – Incapacitating with inability to perform usual activity

#### **8.3.3. Relationship to study medication**

The investigator will determine if there is a reasonable causal relationship between the study medication and an AE or not. The investigator will use her/his best medical judgment and

consider all relevant factors (*e.g.*, temporal relationship, location of the event, the subject's relevant medical history, concomitant therapies and concurrent conditions) to determine the relationship of the AE to the study medication. The investigator will define the relationship of an AE to the study medication by selecting one of the following categories:

**Related** – There is a reasonable causal relationship between the study medication and the AE.

**Not Related** – There is not a reasonable causal relationship between the study medication and the AE.

The expression “reasonable causal relationship” is meant to convey in general that there are facts (evidence) or arguments to suggest a causal relationship (International Conference on Harmonization [ICH] E2A).

### 8.3.4. Procedures for reporting adverse events

At each post-enrollment visit, the investigator will question the subject to elicit AEs using a non-directive question such as “Has there been any change in your health since the previous study visit?” If appropriate, based on the subject's response to non-directed questioning to elicit AEs, the investigator will follow-up with directed questions and appropriate evaluations.

Any AE noted during the reporting period must be reported in the source documents and on the appropriate AE eCRF. AEs that are defined as “Not Related” to the study medications will be followed until they are resolved or until the subject's last study visit. AEs that are defined as “Related” to the study medications will be followed until they are resolved or, if not resolved after the subject's last study visit, until in the opinion of the investigator, the AE reaches a clinically stable outcome with or without sequelae.

### 8.3.5. Procedure for reporting a serious adverse event

Upon becoming aware of a SAE occurring during the AE reporting period, whether or not related to the study medications, the investigator must:

1. Take the appropriate medical action to ensure the subject's safety.
2. Immediately inform the Safety Monitor of the SAE by email, ensuring that the subject information is deidentified (only subject initials and subject number) to: **ProPharma, Email: [[contact]](mailto:[contact])**.
3. Print a copy of the email confirmation from ProPharma and place in the study file.
4. Within 24-hours complete, as fully as possible, an AE eCRF and an SAE form; e-mail the forms and any other relevant information (*e.g.*, concomitant medication eCRF, medical history eCRF, laboratory test results) to ProPharma (Aclaris Therapeutics, Inc. Safety Monitor).
5. Monitor and document the progress of the SAE until it resolves or, if not resolved after the subject's last study visit, until in the opinion of the investigator the SAE reaches a clinically stable outcome with or without sequelae AND the investigator and Aclaris Therapeutics, Inc. Safety and Medical Monitor agree that the SAE is satisfactorily resolved.

6. Inform the Aclaris Therapeutics, Inc. Safety Monitor of SAE updates, via telephone, followed by an SAE form update sent by e-mail.
7. Comply with the appropriate regulatory requirements and Aclaris Therapeutics, Inc. instructions regarding reporting of the SAE to the responsible Institutional Review Board (IRB) or Ethics Committee (EC).

## 8.4. PREGNANCY

### 8.4.1. Definition of Women of Child Bearing Potential (WOCBP)

WOCBP includes any female who has experienced menarche and who has not undergone successful surgical sterilization (*e.g.*, hysterectomy, bilateral tubal ligation, or bilateral oophorectomy) or is not postmenopausal. Postmenopausal is defined as  $\geq 12$  months with no menses without an alternative medical cause. WOCBP must have a negative serum pregnancy test at screening and a negative UPT at Baseline prior to randomization.

### 8.4.2. Highly Effective Methods of Birth Control

The Investigator or subinvestigator will discuss the potential risk factors associated with pregnancy and the importance of maintaining a highly effective method of contraception throughout the study with all WOCBP (for example, those which result in a low failure rate - *i.e.*, less than 1% per year- when used consistently and correctly). All WOCBP must use a highly effective method of birth control during the study and for 30 days after the final dose of study medication in a manner such that risk of failure is minimized.

Highly effective methods include:

- Combined (estrogen and progesterone containing) hormonal contraception associated with inhibition of ovulation:
  - oral
  - intravaginal
  - transdermal
- Progesterone-only hormonal contraception associated with inhibition of ovulation:
  - oral
  - injectable
  - implantable
- intrauterine device (IUD)
- intrauterine hormone-releasing system (IUS)
- vasectomized partner
- sexual abstinence

Vasectomized partner is a highly effective birth control method provided that partner is the sole sexual partner of the WOCBP trial participant and that the vasectomized partner has received medical assessment of the surgical success.

 Sexual abstinence is considered a highly effective method only if defined as refraining from heterosexual intercourse during the entire period of risk associated with the study treatments. The reliability of sexual abstinence needs to be evaluated in relation to the duration of the clinical trial and the preferred and usual lifestyle of the subject.

WOCBP must be on a highly effective method of birth control for the following timeframes prior to study entry:

- Implants (on a stable dose for  $\geq 30$  days)
- Injectables (on a stable dose for  $\geq 30$  days)
- Patches (on a stable dose for  $\geq 30$  days)
- Combined oral contraceptives (on a stable dose for  $\geq 30$  days)
- Intrauterine devices (inserted for  $\geq 30$  days).

Prior to trial enrollment, WOCBP must be advised of the importance of avoiding pregnancy during trial participation and of the potential risk factors associated with pregnancy while in the study. The subject must sign an informed consent form documenting this discussion. During the trial, all WOCBP will be instructed to contact the investigator immediately if they suspect they might be pregnant (*e.g.*, missed or late menstrual period).

If a subject or investigator suspects that the subject may be pregnant prior to study medication administration, the study medication must be withheld until the results of a pregnancy test are available. If pregnancy is confirmed, the subject must not receive study medication and must be discharged from the study.

If, following study medication administration, it is determined that the subject or partner of a male subject may have been or was pregnant at the time of study medication exposure (including 30 days after study medication administration) the investigator must immediately notify the Aclaris Therapeutics, Inc. Medical Monitor and record the event on a pregnancy surveillance form. While not an AE or SAE, the investigator must report every pregnancy using a pregnancy surveillance form and follow the reporting procedures described for SAE reporting.

Protocol-required procedures for trial discontinuation and follow-up must be performed on the subject unless contraindicated by pregnancy (*e.g.*, x-ray studies). Other appropriate pregnancy follow-up procedures should be considered if indicated. In addition, the investigator must report to Aclaris Therapeutics, Inc.'s Medical Monitor on the pregnancy surveillance form, follow-up information regarding the course of the pregnancy, including perinatal and neonatal outcome. Infants should be followed for a minimum of six weeks.

## 9. STATISTICS

### 9.1. Sample Size and Power Calculations

The planned sample size is 95 enrolled subjects with approximately 45 subjects enrolled with AT or AU.

The sample size estimate was based on published results from a similar study (Crispin et al. 2016) where 32% of subjects receiving active drug achieved at least a 50% reduction in hair loss (SALT50) under similar conditions. For the current study, the primary efficacy analysis is mean percent change in hair loss, evaluated using SALT scores. That analysis is expected to have greater statistical sensitivity than the SALT50 responder analysis, which is also a secondary efficacy analysis in the current study.

We assume the pooled results of 600mg and 800mg treatment groups in the current study will achieve the same or higher SALT50 response rate (32%) as the published results above, and pooled Vehicle plus 400mg treatment groups will not achieve more than a 6% SALT50 response rate. Based on a comparison of those two pooled groups, the current study is anticipated to have no less than 80% power with a 10% subject dropout rate for the SALT50 analysis. Because the primary efficacy analysis of mean percent change in hair loss using SALT scores is expected to be more sensitive than the SALT50 responder analysis, the power for the primary analysis is also expected to be no less than 80%.

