**Statistical Methods:****Sample Size/ Power Calculations**

The planned sample size is approximately 95 enrolled subjects with approximately 45 subjects enrolled with AT or AU. The sample size estimate was based on published results from a similar study (Crispin et al. 2016) where 32% of subjects receiving active drug achieved at least a 50% relative reduction in hair loss (SALT50) under similar conditions. For the current study, the primary efficacy analysis is mean % change in hair loss, evaluated using SALT scores. That analysis is expected to have greater statistical sensitivity than the SALT50 responder analysis, which is also a secondary efficacy analysis in the current study.

We assume the pooled results of 600mg and 800mg treatment groups in the current study will achieve the same or higher SALT50 response rate (32%) as the published results above, and pooled Vehicle plus 400mg treatment groups will not achieve more than a 6% SALT50 response rate. Based on a comparison of those two pooled groups, the current study is anticipated to have no less than 80% power with a 10% subject dropout rate for the SALT50 analysis. Because the primary efficacy analysis of mean percent reduction in hair loss using SALT scores is expected to be more sensitive than the SALT50 responder analysis, the power for the primary analysis is also expected to be no less than 80%.

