### 9.4.1. Primary Efficacy Analyses

The primary efficacy variable will be the percent change from Baseline (Visit 2) in the SALT score at Visit 9 (Week 24). Missing data for the primary endpoint will be imputed using Last Observation Carried Forward (LOCF) methodology. The analysis will be conducted on the percent change from baseline over time including all visits using a mixed effect model repeated measures (MMRM). The adjusted mean (LS Mean) for percent change from baseline in the SALT score at each visit, estimated from the MMRM, with the estimated standard error and 95% confidence interval (CI), will be presented in tabular and graphic format. The difference in the adjusted means between treatment groups and the associated 95% CI of the difference will be provided. No adjustment for multiplicity will be made. The model will include fixed effect terms for treatment, study visit, baseline SALT score group (<50, ≥50), and treatment by SALT group interaction. The primary analysis will be based on the Intent-to-Treat (ITT) population. Statistical significance for primary efficacy endpoint will be declared if at least one treatment group comparison at the Week 24 visit has a two-sided p-value less than or equal to 0.05.

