## **4. GENERAL STATISTICAL CONSIDERATIONS**

### **4.1. SAMPLE SIZE AND POWER**

The planned sample size is 95 enrolled subjects with approximately 45 subjects enrolled with AT or AU. It is assumed that the proportion of subjects who achieve at least a 50% reduction in hair loss (SALT50) for the pooled 600mg and 800mg treatment groups will be at least 32%, and the SALT50 for the pooled placebo and 400mg treatment groups will be at most 6%. Assuming a 10% dropout rate, this results in >80% power for the SALT50 analysis. Because the primary efficacy analysis of mean percent change in hair loss using SALT scores is expected to be more sensitive than the SALT50 responder analysis, the power for the primary analysis is also expected to be no less than 84%.

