## **6. STATISTICAL METHODS**

Descriptive statistical methods will also be used to summarize the data from this study, with hypothesis testing performed for the primary and key secondary efficacy endpoints. Unless stated otherwise, the term “descriptive statistics” refers to number of subjects, mean, median, standard deviation, minimum, and maximum for continuous data, and frequencies and percentages for categorical data. For categorical variables, the denominator of percentages will be the number of subjects in the treatment group, except for those collected by study visit and/or scheduled time point, in which case the denominator of percentages will be the number of subjects with a non-missing value at the visit and/or the scheduled time point. If a different denominator is used, this will be identified in the summary table.

All data collected during the study will be included in data listings. Unless otherwise noted, the data will be sorted first by treatment group, subject number, and then by date within each subject number.

The term ‘treatment group’ refers to ATI-501 active groups and matching Placebo Oral Suspension group.

All statistical testing will be two-sided and will be performed using a significance (alpha) level of 0.05 unless otherwise stated. P-values will be presented to three decimal places. For the efficacy

endpoints, the ATI-501 treatment groups will be tested versus Placebo Oral Suspension via statistical inference.

The statistical analyses will be conducted with the SAS® software package version 9.4 or higher. All analyses will be subject to formal verification procedures. Specifically, results will be independently verified by a second programmer/statistician prior to issuance of the draft statistical report. All documents will be reviewed by the lead statistician to ensure accuracy and consistency.

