#### **6.2.5. Secondary Efficacy Analysis**

Descriptive statistics will be presented for all secondary efficacy endpoints.

The mean percent change from baseline in the ALODEX score (percent regrowth); the mean change from baseline in SALT and the mean change from baseline in ALODEX will be analyzed using the methods planned for the primary efficacy analysis. The calculated DLQI total score ranges from 0 to 30. This mean change from baseline in DLQI will also utilize the MMRM analysis as planned for the primary efficacy analysis.

Responder-type analyses are planned based on the SALT, ALODEX, Scalp-ClinRO, and Scalp-PRO. The responder definitions include:

- The proportion of subjects achieving a  $\geq 50\%$  hair regrowth compared with baseline for SALT and for ALODEX scores
- Proportion of subjects achieving an absolute SALT score  $\leq 10$
- Proportion of subjects with  $\geq 2$ -point improvement in Scalp-ClinRO for the Target Area (patchy AA subjects only)
- Proportion of subjects with  $\geq 2$ -point improvement in Scalp-PRO for the Target Area (patchy AA subjects only)
- Proportion of subjects with  $\geq 1$ -point improvement in Scalp-ClinRO for the entire scalp
- Proportion of subjects with  $\geq 1$ -point improvement in Scalp-PRO for the entire scalp

The observed proportion of responders and associated 95% CI will be presented. Adjusted rates and 95% CI will be obtained from a logistic regression model with a factor for treatment. The p-value for the overall global test that  $\beta=0$  for this factor will be presented. The adjusted odds ratios (95% CI) for being a responder (active/placebo oral suspension) will be presented along with the associated p-value.

The questionnaires Scalp-PRO, Scalp-ClinRO, PhGIS, AFHA, and SGIS are collected on a 1-5 scale. The SGRHQ questionnaire is collected on a 1-7 scale. The frequency of responses for each value will be reported by visit and treatment group. Additionally, change status will be categorized as “Better by x points” when the score decreases from baseline by x points, and as “Worse by x points” when the score increases by x points. For these scales, a Wilcoxon rank sum test will be used at each visit to obtain a p-value to compare the change status of each active treatment group to the placebo oral suspension.

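### The stated power (80% in the protocol, 84% in the SAP) is for a pooled SALT50 contrast that no planned analysis makes, and nothing in the documents supports it for the primary endpoint

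*Protocol*

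**What the plan says.** **Power calculation.** Protocol 9.1 and the Synopsis assume that 600 mg and 800 mg, pooled, reach a SALT50 rate of at least 32%. On the other side, "pooled Vehicle plus 400mg treatment groups will not achieve more than a 6" per cent. SAP 4.1 words the control side as "for the pooled placebo and 400mg treatment groups will be at most 6" per cent. With 95 enrolled and 10% dropout, the protocol concludes: "Based on a comparison of those two pooled groups, the current study is anticipated to have no less than 80% power". SAP 4.1 gives more than 80% for SALT50.

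**Transfer to the primary endpoint.** Both documents argue that mean percent change in SALT should be a more sensitive analysis than the responder analysis. From this the protocol infers that "the power for the primary analysis is also expected to be no less than 80" per cent, and the SAP that "the power for the primary analysis is also expected to be no less than 84" per cent. Neither gives a mean difference, an SD or a distribution.

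**Planned tests.**
- Primary (Protocol 9.4.1): "Statistical significance for primary efficacy endpoint will be declared if at least one treatment group comparison at the Week 24 visit" has a two-sided p-value of 0.05 or less, without multiplicity adjustment.
- All efficacy endpoints (SAP 6): "the ATI-501 treatment groups will be tested versus Placebo Oral Suspension via statistical inference".
- Responders (SAP 6.2.5): a logistic model with a treatment factor, its global test, and odds ratios "for being a responder (active/placebo oral suspension) will be presented along with the associated p-value".
- The tables and figures in SAP 9 include none that pools 600 with 800 mg or 400 mg with placebo.

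**Sample size.** The Synopsis Methodology has 80 randomised, about 40 of them AU or AT. The Synopsis sample-size text, Protocol 9.1 and SAP 4.1 have 95, about 45 of them AT or AU.

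**The concern.** A power statement should describe a test that will be run. This one differs from the planned tests in two ways. It pools arms that the analysis keeps apart, placing 400 mg on the control side when every planned test treats it as an active group. And it is worked out for a secondary binary endpoint and then attached to the primary continuous one.

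A reader would take 80% or 84% as the power of the primary analysis, and might judge a non-significant dose against that figure. The documents give no basis for doing so. They also give two different figures for the same analysis, with no input to explain the rise from 80 to 84.

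**Working it through.** **Inputs.** N = 95, allocation 1:1:1:1, 10% dropout, and rates of 32% and 6% for the pools (Protocol 9.1, SAP 4.1). Two-sided 0.05 (SAP 6). Per-arm rates are not in the documents and are assumptions below. All SALT50 pairwise and pooled powers are exact binomial enumerations: the sum of P(a)P(b) over all outcomes (a, b) for which the test rejects.

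**1. The plan's own figure.** 95 × 0.9 = 85.5, or 42.75 per pooled side (43 v 43). At 32% v 6%, power is 84.4% by Fisher and 91.0% by chi-square. The 80% floor holds for the pooled contrast. The SAP's 84% matches the Fisher value, but the documents name no test, so that origin is an inference.

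**2. At the other sample size.** 80 × 0.9 = 72, or 36 v 36. Fisher gives 76.6% and chi-square 84.8%. On 80 subjects the pooled figure is below 80% under one test and above it under the other.

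**3. SALT50, one dose at 32% v placebo.** Per arm, 85.5/4 ≈ 21 after dropout and 95/4 ≈ 24 without.

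| Assumed placebo rate | Fisher, 21 to 24 per arm | Chi-square, 21 to 24 per arm |
|---|---|---|
| 6% | 48% to 57% | 62% to 69% |
| 4% | 59% to 68% | 73% to 79% |
| 3% | 65% to 74% | 78% to 84% |
| 1% | 78% to 87% | 89% to 93% |
| 0% | 85% to 92% | 94% to 97% |

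The pooled values for comparison are 84% and 91%. Down to 3%, one dose v placebo has less power than the pooled contrast under the same test. At 1% it overtakes with 24 per arm, and at 0% it does so with either size.

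Two further SALT50 figures:
- At least one of 600 and 800 mg significant, both at 32% and placebo at 6%: 65-74% (Fisher) or 78-84% (chi-square).
- The planned four-arm global test at 6%, 6%, 32%, 32% (200,000 simulations): 75-82% (score) or 80-85% (likelihood ratio), close to the stated figure.

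**4. Primary endpoint.** No power can be computed from the documents. As an illustration only, take a two-sample t-test at Week 24 (not the MMRM), with 32% and 6% of subjects beyond 50% regrowth, 600 and 800 mg equally effective, and a shared placebo arm. Three assumed distributions give these standardised differences:
- (a) Normal, equal SD: z(0.94) − z(0.68) = 1.09.
- (b) Regrowth of 0% or 100%: (0.32 − 0.06)/√[(0.32×0.68 + 0.06×0.94)/2] = 0.26/0.370 = 0.70.
- (c) Responders uniform on 50-100%, others uniform on 0-50%: the means are 41 and 28, each variance is 50²/12 + 2500p(1−p), and the difference is 13/23.5 = 0.55.

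| Distribution | At least one dose significant, 21 to 24 per arm | One given dose significant, 21 to 24 per arm |
|---|---|---|
| (a) | 98% to 99% | 93% to 96% |
| (b) | 78% to 83% | 62% to 69% |
| (c) | 59% to 65% | 42% to 47% |

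The first results column follows the protocol's success rule. The same responder rates are thus compatible with primary power well below or well above 80%. Against the one-dose chi-square power at placebo 6% (62-69%), the continuous analysis is more sensitive under (a), about equal under (b) and less sensitive under (c).

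**The case against.** The strongest reply is that this is an initial Phase 2 study, described in the amendment history as sized to explore. The documents disclose the pooled basis openly and hedge with words of expectation, and confidence intervals for the treatment differences are planned. That limits the consequences, and no analysis changes. It does not remove the point, because the protocol sets a formal significance rule for the primary endpoint and both documents attach a number to its power.

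Three stronger readings are tempting, and the documents do not support them.
- **That the trial is underpowered.** The success rule needs only one significant comparison, which raises power. Scenario (c) is a harsh one: it gives placebo a mean regrowth of 28% in a population enrolled as stable, and gives the drug no effect below the 50% threshold. The primary analysis uses ITT with LOCF, so dropouts who have post-baseline data stay in, and 21 per arm may be pessimistic. The planned global responder test is near the stated power.
- **That one dose against placebo always has less SALT50 power than the pooled contrast.** The 6% is a ceiling on the placebo and 400 mg pool, and no lower limit is set for placebo alone. The shortfall shrinks as that rate falls and is gone near 0-1%. Nor does the plan say that 600 and 800 mg share the 32% equally.
- **That the SAP took its 84% from a Fisher calculation.** The numbers agree, but no test is named.

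**Conclusion.** The point holds as a fault in the stated justification. The only power calculated is for a pooled SALT50 contrast that is not a planned analysis. The primary figure is carried over by assertion, without a mean difference or SD, and differs between the protocol (80%) and the SAP (84%). Primary power is unsupported; it is not shown to be either low or adequate.

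The illustrative 59-99% for at least one dose rests on assumed distributions, a t-test in place of the MMRM, and equal effects of 600 and 800 mg. The SALT50 figures of 48-57% and 62-69% rest on 32% for the dose and 6% for placebo alone, which the plan does not state. The conflict between 80 and 95 subjects is separate but bears on the same number, since at 80 the pooled Fisher power (77%) is below the stated floor.

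**What to change.** In Protocol 9.1, the Synopsis and SAP 4.1:
1. Label the pooled SALT50 figure as power for a contrast that is not a planned analysis.
2. Delete the 80% and 84% claims for the primary analysis, or replace both with one figure derived from a stated mean difference and SD under the rule that one significant comparison suffices.
3. If a SALT50 power is kept, give it for the planned active-versus-placebo contrasts, with the assumed per-arm rates and the test named.
4. Reconcile 80 randomised (40 AU or AT) in the Synopsis Methodology with 95 (45) elsewhere.

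The cost is wording and one recalculation. The stated power may become less favourable. No subjects are added and no analysis changes.
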